2 PROJECT OBJECTIVES AND DESIGN

2.1 Objectives and Hypothesis

- i) To determine the extent of infection in the special population of police officers of the canton Bern. We hypothesize that the COVID-19 seroprevalence within the police department will be between 1% and 2% at the beginning of the study. We further hypothesize that the seroprevalence will increase during the study period by 8% (i.e., from 2% to 10%). The rationale for this increase proportion derives from the Geneva study, and the ongoing COVID-19 pandemic till the end of study period [11].
- ii) To determine risk factors for infection by comparing the proportion of seropositivity (infected versus noninfected individuals). We hypothesize that police officers with fieldwork activity will have a higher seroprevalence than will office and administration personnel. We hypothesize that working in the city of Bern will be associated with a higher seroprevalence than will working in other geographic areas of the canton (i.e. rural area).
- iii) To monitor COVID-19 antibody titres and neutralizing capacity over time and to associate them with reinfection rates and infection-free intervals in police officers after accidental contact with a proven COVID-19 case. We hypothesize that in seropositive individuals, there will be a decreasing dynamic of antibody titres over the one-year study period, and hence, a decrease of neutralizing capacity.

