2.2 Primary and secondary endpoints

Primary endpoint: The variable of primary interest is **COVID-19 seropositivity**. This variable is measured at five time points over the one-year study period. The following baseline factors may have an influence on the primary endpoint and will be obtained: (i) pre-existing comorbidities, (ii) rural versus city distribution of working place, and (iii) office work versus field work.

Secondary endpoints: We will assess the proportion of symptomatic and asymptomatic cases among seropositive participants. We will calculate the attack rate in different subgroup. These include (i) study participants with health-related risk factors (age>50 and age>60 years, diabetes, arterial hypertension, cardiovascular disease, chronic pulmonary disease, immune-compromised status due to host diseases, medical treatment, cancer, obesity), (ii) activity-related subgroups (i.e. fieldwork vs office activity), (iii) geography-related subgroups (i.e. city vs rural areas). In follow-up visits, the antibody titers (i.e. dynamic) and the neutralization capacity will be assessed. Thereby we will determine the change in serum levels of SARS-CoV-2 antibodies over time in seropositive participants.

2.3 Project design:

This is a single center special population (i.e. police officers of the canton of Bern) seroprevalence survey. It is a repeated cross-sectional investigation in the canton of Bern combined with a longitudinal cohort study with serial sampling of the included study participants. The protocol is aligned with the one of seroprevalence studies recommend by the WHO [25].

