Each sample will be labelled with the study participant's code immediately prior to blood withdrawal. For each serum sample collected, the time of collection, the conditions for transportation, and the time of arrival at the study laboratory will be recorded. Given the efficient means of transport in the canton of Bern, we anticipate that serum samples will reach the laboratory within the same day after collection. They will be aliquoted and stored at our at the Interregionale Blutspende SRK (-30°C), for coordinated analysis of batches. The diagnostic laboratories of both the Interregionale Blutspende SRK and the IFIG have the required government permits to operate a diagnostic service for clinical specimens of human origin, including storage of such specimens; furthermore, they are accredited to the ISO/IEC 17025 Standard.

On each sample two commercially available SARS-CoV-2 serological assays will be performed (Elecsys® Anti-SARS-CoV-2-Test). According to the manufacturer's information, the specificity is 99.81 % (95% CI 99.65 – 99.91 %) and sensitivity 100 % (88.1 – 100 %), respectively. The rationale for using this particular test includes a performance evaluation at the Interregionale Blutspende SRK that demonstrated a high specificity (Riester et al. medRxiv 2020.08.07.20169987). Overall specificities for the Elecsys Anti-SARS-CoV-2 immunoassay in 9575 samples from blood donors (n = 6714) and routine diagnostic testing specimens (n = 2861) were 99.82% (95% CI 99.69-99.91) and 99.93% (95% CI 99.75-99.99), respectively. In addition, the test will be purchased to a reasonable price. The rationale for choosing two commercially available SARS-CoV-2 serological assays is the following. One test detects anti-nucleocapsid antibodies, while the other detects anti-spikeprotein antibodies. Anti-nucleocapsid antibodies detect antibodies derived from natural infection but do not detect antibodies derived from mRNA-vaccination. It is important for both the investigator and the study participant to identify antibodies derived from vaccination. Therefore, we complement the tests for anti-nucleocapsid antibodies with tests for anti-spike-protein antibodies. Testing will be carried out at the Interregionale Blutspende SRK.

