In serum samples with positive antibody test, quantification of neutralizing antibodies will be performed at the IFIG. They will be measured by pre-incubating serial dilutions of baseline and convalescent serum with 200 to 400 plaque forming units (PFU) of SARS-CoV-2, after which a PFU reduction assay will be performed on Vero-E6 cells. After 2 days, cells will be fixed and stained with crystal violet to analyse the neutralizing capacity of antibodies generated towards SARS-CoV-2, as previously described [26].

The results of Anti-SARS-CoV-2-Test of will be communicated to study participant via e-mail within 2 weeks of blood sampling. The results of neutralization capacity will be communicated at the end of the study period. This experimental assay will be performed in the research laboratory with all positive samples during one month, at the end of the study period.

Seropositive participants or participants with a positive SARS-CoV-2 test in the past (PCR or antigen test) will be asked to complete an additional questionnaire that investigates possible contacts (i.e., working versus private environment) and sources of transmission (see point 5 in the BASEC application: "CASE REPORT FORM").

Seropositive participants or vaccinated participants will be contacted by the study team within 4 weeks after laboratory result, for one additional blood sampling that investigates neutralization capacity. Seropositive participants with vaccination will be contacted twice. Figure 2 illustrates the sampling scheme.

Antibodies	Vaccine	No. of blood sampling in 1 year
		
negative	no	5 baseline + every 3 months
positive	no	6 baseline + every 3 months + 1 sampling
negative	yes	6 baseline + every 3 months + 1 sampling
positive	yes	7 baseline + every 3 months + 2 samplings

Figure 2: Schematic overview of the blood sampling over one year

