At every visit, we will first calculate the crude seroprevalence as the proportion of the seropositive samples among all collected samples. Second, we will adjust the seroprevalence for test characteristics (false positive and false negative rate). Third, we will calculate the weighted seroprevalence to adjust for sampling imbalances, with weighting factors based on the demographic structure of the police force (age, sex, rural vs. city distribution). We will furthermore analyze changes in seropositivity in a repeated-measures mixed-effects logistic regression model. In a second step, we will include health-related, activity-related and geography-related risk factors as covariates into the model to study effects of these factors and derive corresponding odds ratios. Change of risk factors over time will be accounted for. The change of antibody titres over time will also be analyzed using mixed models.

In addition to demographic characteristics, a descriptive analysis of health-related variables (i.e. diabetes, arterial hypertension, cardiovascular disease, chronic pulmonary disease, immunocompromised status because of host diseases or medical treatment, cancer, obesity), and activity-related data (i.e. fieldwork activity vs office and administration activity, working in cities or rural areas) will be performed. The categorization of variables is illustrated in appendix 2. Comparison of categorical and continuous variables will be performed with chi-square tests, t-tests, Wilcoxon-Mann-Whitney-Test, Kruskal-Wallis-Test and multivariate analysis, accordingly. The significance level will be two-sided $\alpha = 0.05$.

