Appendix 2: The categorization of variables

Parameter	Definition	Source of data to calculate the parameters
Cumulative incidence	The proportion of individuals with seropositivity	Laboratory result
Age- and gender specific attack rate	The proportion of individuals per age and gender strata with seropositivity	Laboratory result Questionnaire
Symptomatic proportion of cases	The proportion of individuals with seropositivity who showed symptoms or signs of COVID-19 infection (+/- confirmed PCR result in the past)	Questionnaire
Asymptomatic proportion of cases	The proportion of individuals with seropositivity who showed no symptoms or signs of COVID-19	Questionnaire
Attack rate in risk group (health-related data) (Persons over 65 years are not included because retirement is expected at this age in the study population).	Study participants with one or more of the following risk factors: diabetes, arterial hypertension, cardiovascular disease, chronic pulmonary disease, immuno-compromised because of host diseases or because of medical treatment, cancer, obesity (BMI > 30 kg/m ²)	Laboratory result Questionnaire
Activity related cumulative incidence	The proportion of individuals with seropositivity in the following 2 groups: Group 1: Police officers with fieldwork activity and frequent population contact. Group 2: office and administration occupation with low population contact.	Laboratory result Questionnaire
Geography related cumulative incidence	The proportion of individuals with seropositivity in the following 2 groups: Group 1: occupation in cities (Bern, Thun, Biel) Group 2: occupation in rural area of Bern or in cities but not belonging to group 1.	Laboratory result Questionnaire
Sub-study in seropositive study participants		
Parameter	Definition	Source of data to calculate the parameters
Serological response to infection	The change in serum level of specific antibodies to COVID-19 virus (increase in antibody titres)	Laboratory result over time
Seropositive result confirmation (specificity)	Seropositive result at baseline or seroconversion during the study year that will be confirmed with two additional serum samples, two and four weeks after the positive antibody result.	Laboratory result
Work or social environment-related exposure	Study participants perception of possible COVID-19 exposure	Questionnaire

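### The titre analysis has no assay or vaccination rule, so anti-spike and neutralisation rises after a vaccine dose would count as response to infection and understate or reverse the decline hypothesised in objective iii

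*Combined protocol and SAP*

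**What the plan says.** **The hypothesis.** Section 2.1, objective iii, expects that "in seropositive individuals, there will be a decreasing dynamic of antibody titres over the one-year study period, and hence, a decrease of neutralizing capacity". Section 2.2 sets the matching secondary endpoint: "Thereby we will determine the change in serum levels of SARS-CoV-2 antibodies over time in seropositive participants". Neither says which antibody is meant, or what happens to a participant's series after a vaccine dose.

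**The definition.** In Appendix 2, in the sub-study of seropositive participants, the response to infection is "The change in serum level of specific antibodies to COVID-19 virus (increase in antibody titres"). The only data source given is the laboratory result over time.

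**The model.** Section 4.1 says: "The change of antibody titres over time will also be analyzed using mixed models". It names no assay and no covariate. Just before this it states "Change of risk factors over time will be accounted for", but that belongs to the seropositivity model, whose listed factors are health, activity and geography. Vaccination is not among them.

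**What the design knows about vaccination.** Section 3.3 states: "Anti-nucleocapsid antibodies detect antibodies derived from natural infection but do not detect antibodies derived from mRNA-vaccination". The anti-spike test is added for this reason: "It is important for both the investigator and the study participant to identify antibodies derived from vaccination". Vaccinated people stay in follow-up: "Seropositive participants or vaccinated participants will be contacted by the study team within 4 weeks after laboratory result". Figure 2 has a row for participants who are antibody-positive and vaccinated, with seven draws in the year. Neutralisation is run on all positive samples. Section 6.1 treats immunity after exposure and immunity after vaccination as two separate interests.

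**The concern.** The design collects what is needed to tell infection from vaccination: two assays, and a vaccination status that drives the extra draws. Neither the definition nor the titre model uses it. An infected participant who is vaccinated at month 6 will tend to show higher anti-spike and neutralisation levels at months 6, 9 and 12. Under Appendix 2 that rise is a response to infection. Under section 4.1 nothing takes it out of the slope.

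Objective iii is about waning. Rises placed late in the year lift the estimated slope, so waning looks slower than it is, or absent. Section 1.2 wants to learn how long antibodies persist after infection, and a slope that mixes in vaccine boosts does not answer that.

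**Working it through.** The documents state no expected titre change, so there is no plan figure to reproduce. The check is on direction first, then on size under stated assumptions.

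**Inputs from the protocol**
- 1,000 participants; seroprevalence rising from 2% to 10% (section 4.1), so 20 seropositive at baseline and 100 at the end.
- Five visits, at months 0, 3, 6, 9 and 12 (section 3.3).
- Repeat draws 2 and 4 weeks after the first positive result (section 3.3, Appendix 1, Appendix 2).

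**Assumptions (not in the documents)**
- 20 new positives at each of visits 2 to 5.
- Doses spread evenly over 12 months; uptake u of 25% to 90%.
- Boost of 4- to 16-fold; half-life of 3 to 6 months, base case 4, so the true 12-month change is -12/4 = -3.0 log2.

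**1. Direction.** With visits at 0, 3, 6, 9 and 12, the squared deviations from month 6 sum to 36 + 9 + 0 + 9 + 36 = 90. A step of size b from month 3 changes the fitted 12-month slope by 12 × (-3 + 0 + 3 + 6)/90 × b = 0.8b. From month 6 or month 9 it is 12 × 9/90 × b = 1.2b, and from month 12 it is 12 × 6/90 × b = 0.8b. All are positive, so a boost always pushes the slope up.

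**2. Size.** The upward bias over 12 months is about u × log2(fold). Simulation with staggered seroconversion gives roughly 0.9 of that. It used 100 participants, a random-intercept model, time counted from the first positive sample, between-person SD 1 and residual SD 0.5 log2, and 40 runs per cell. The truth is -3.0:

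| Uptake | Boost | Formula | Time-only model |
|---|---|---|---|
| 25% | 4-fold | -3 + 0.25 × 2 = -2.5 | -2.54 |
| 50% | 8-fold | -3 + 0.50 × 3 = -1.5 | -1.61 |
| 90% | 8-fold | -3 + 0.90 × 3 = -0.3 | -0.57 |
| 90% | 16-fold | -3 + 0.90 × 4 = +0.6 | +0.20 |

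The bias does not depend on half-life, so the ends of the range follow directly.
- Half-life 3, 25%, 4-fold: true change -4.0, bias 0.46, and 0.46/4.0 is about 12% of the decline lost.
- Half-life 6, 90%, 8-fold: true change -2.0, bias -0.57 + 3.0 = 2.43, estimate +0.43.
- With no vaccination the bias is zero.

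**3. Which repair works.** If titres decay at the same rate before and after a dose, a vaccinated yes/no term recovers -3.00 to -3.02, and pre-dose samples alone recover -2.96 to -3.00. The two separate when decay after a dose differs. With an 8-fold boost, 90% uptake and post-dose half-lives of 2 and 8 months:
- yes/no term only: -4.49 and -2.27;
- yes/no term plus its interaction with time: -3.38 and -2.76 (a second run gave -3.27 and -2.82);
- pre-dose samples only: -3.00 and -2.96 at 50% and 90% uptake (post-dose decay cannot affect them); the second run at 90% gave -2.90 and -2.98.

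In that second run the spread of the interaction model and of the pre-dose analysis was equal (0.24 and 0.24; 0.16 and 0.16). The interaction model therefore gains no precision for the decline and carries more bias.

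**4. What the pre-dose analysis keeps.** With the two repeat draws there are 300 visit samples (20 × (5 + 4 + 3 + 2 + 1)) plus 100 × 2 = 200 repeats, 500 in all.
- If everyone were vaccinated, the pre-dose visit samples are 20 × 1 + 40 × 0.75 + 60 × 0.5 + 80 × 0.25 + 100 × 0 = 100. The pre-dose repeats are 20 × (22.5 + 16.5 + 10.5 + 4.5)/12 = 90. Together that is 190.
- Samples kept: (1 - u) × 500 + u × 190 = about 423, 345 and 221 at u = 25%, 50% and 90%.
- Two or more pre-dose samples requires a dose later than half a month after the first positive: 20 × (11.5 + 8.5 + 5.5 + 2.5)/12 = 46.7 of 100 if all are vaccinated. So (1 - u) × 100 + u × 46.7 = about 87, 73 and 52 participants.

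**The case against.** **The row is labelled as a response to infection, and Figure 2 has an antibody-negative, vaccinated row, so seropositive probably means infected.** That is a fair reading of intent, and it would keep people who were only vaccinated out of the series. It does not help with those infected first and vaccinated later. They are the last row of Figure 2, they stay in the series, and their anti-spike level can rise after a dose.

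**The Appendix 2 row does not set the slope.** This stands. The row concerns an increase; the one-year change comes from sections 2.1 and 2.2 and the sentence in 4.1. Rewording the row alone would leave the model untouched, so 4.1 has to change too.

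**Section 4.1 never says that time is the only term.** Also true. A reader might infer that the plan commits to a time-only model, or that it overlooks vaccination. The documents support neither: 4.1 is silent on covariates for titres, and section 3.3 handles vaccination with care in sampling and testing. What stands is that nothing commits the analyst to a rule, and the choice of assay, samples and terms is left until the titres are known.

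**Section 6.2 says that comparing responses before and after vaccination, using stored serum and a later sample, needs a new ethics proposal.** This limits the fix. Taking post-dose samples out of the decline estimate is unaffected; a separate post-vaccination report may not be. Sections 3.3 and 6.1 point the other way, so the sponsor should settle it.

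**Conclusion.** The point holds, at modest weight, for one secondary objective. The anti-spike and neutralisation slopes are open to an upward bias, which understates the decline. The direction follows from the design, given only that a dose raises these levels. Section 3.3 implies this for anti-spike; for neutralisation it is an assumption, though the extra draws for vaccinated participants presuppose that it is of interest.

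The size is illustrative. Over the assumed ranges it runs from about 12% of the decline lost to a change of sign. A reader might infer that the decline will in fact vanish, but the documents give no uptake, boost or half-life, so that cannot be claimed.

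A reader might also extend the point to all antibody results. The documents do not support that. By section 3.3 the anti-nucleocapsid series is not affected by mRNA vaccination (nothing is said of other vaccine types), and the primary endpoint, a proportion seropositive, is not part of this point.

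**What to change.** 1. **Appendix 2:** define the serological response to infection as the change in anti-nucleocapsid level in anti-nucleocapsid-positive participants.
2. **Section 4.1, main analysis:** for anti-spike and neutralisation, estimate the objective iii decline in anti-nucleocapsid-positive participants from samples taken before the first reported vaccine dose, including the 2- and 4-week repeat draws.
3. **Section 4.1, sensitivity analysis:** use all samples, with a time-varying vaccination term and its interaction with time.
4. **Post-dose samples:** keep them out of the infection-decline estimate. Before adding any separate post-vaccination description, check it against section 6.2.

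**Cost.** One definition and two or three sentences, with no new draw or assay. The contact rule in section 3.3 already needs vaccination status. The questionnaire is not in the documents, so confirm that status and date of first dose are recorded at every visit.

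The price is fewer samples: under the assumptions above, about 423, 345 or 221 of 500 are kept at 25%, 50% or 90% uptake. These counts rest on the two repeat draws. Section 3.3 also describes a single extra draw, so the schedule should be confirmed. The pre-dose analysis further assumes that the timing of vaccination does not depend on unmeasured titre; the sensitivity analysis gives a partial check.
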